## 5.2. Inclusion – Exclusion Criteria and General Study Population

The study population will consist of healthy male or female subjects  $\geq 18$  years of age with presence of moderate DED in at least one eye [REDACTED]. Approximately 84 subjects will be enrolled in total between Parts 1 and 2. Written informed consent will be obtained from each subject.

The full inclusion and exclusion criteria defined in the protocol apply to all subjects and are not repeated herein. Reference is made to the final protocol for the specific inclusion and exclusion criteria for study subjects.

## 5.3. Randomization and Blinding

Prior to initiation of study drug dosing, 2:1 randomization (INV-102: vehicle) will occur by site personnel [REDACTED] once it is confirmed that the subject meets the study entry criteria. [REDACTED] will provide the subject identification number listed on all study documents and used to manage the randomization and study drug assignment based on a central randomization scheme [REDACTED]. Study drug will be labeled with medication kit (bottle) numbers, and [REDACTED] will provide each site with the specific medication kit number for each randomized subject at the time of randomization.

Study drug will be masked to both Investigator and study subjects, as well as Invirsa. The individual treatment assignments will be masked to the Investigator, Invirsa, and the subjects.

## 5.4. Analysis Variables

The following efficacy variables will be collected [REDACTED]:

- Eye Dryness Composite Score (combines the change in eye dryness score from the [REDACTED] DED symptom VAS plus the change in corneal fluorescein staining)
- Eye Discomfort Composite Score (combines the change in eye discomfort score from the [REDACTED] DED symptom VAS plus the change in corneal fluorescein staining)
- Changes in VAS (individual item scores and overall score [sum [REDACTED]])

[REDACTED]

[REDACTED]

- Changes in corneal fluorescein staining [REDACTED]

[REDACTED]

[REDACTED]

[REDACTED]

[REDACTED]

The Eye Dryness Composite Score and the Eye Discomfort Composite Score will each be a combination score of the VAS (either the "eye dryness score" or the "eye discomfort score") change from Baseline and corneal fluorescein staining change from Baseline using the following equation:

[REDACTED]

[REDACTED]

The following safety variables will be collected in Parts 1 and 2, unless as described below:

- TEAEs
- Vital signs
- Best-corrected visual acuity
- Slit lamp examination findings
- [REDACTED]
- Intraocular pressure (Part 1 only)
- Fundus examination (Part 1 only)
- Pachymetry (Part 1 only)
- Endothelial cell count (Part 1 only)
- Corneal fluorescein staining (Part 1 only)

■ [REDACTED]

■ [REDACTED]

■ [REDACTED]

■ [REDACTED]

## **6. SAMPLE SIZE**

Part 1 (Dose Escalation): The sample size of approximately 9 subjects each in Cohorts 1 to 4 (6 active: 3 vehicle) is considered sufficient for evaluation of safety, tolerability, and PK of each cohort. The sample size is not based on statistical power considerations.

Part 2 (Optional Dose Expansion): The sample size of approximately 48 subjects in Cohort 5 (32 active: 16 vehicle) is considered sufficient for evaluation of preliminary efficacy of INV-102. The sample size is not based on statistical power considerations.

## **7. GENERAL CONSIDERATIONS**

### **7.1. Analysis Populations**

The following analysis populations will be defined for this study.

#### **7.1.1. Modified Intention-to-Treat (mITT)**

The mITT population will include all randomized subjects who received at least 1 drop of study drug in the Study Eye and completed at least 1 scheduled post-dosing assessment in the Study Eye. The mITT population will be used to analyze all efficacy endpoints, with subjects included in their randomized study drug regardless of the study drug they actually received.

#### **7.1.2. Per Protocol Population (PP)**

The PP population includes all subjects in the mITT population who have study drug compliance of  $\geq 80\%$  as defined by [REDACTED], and have no major protocol deviations considered to have significant impact on study drug outcome. The PP population will be used to analyze primary and secondary efficacy endpoints.

#### **7.1.3. Safety Population (SP)**

The safety population (SP) will include all randomized subjects who received at least 1 drop of study drug. The safety population will be used to summarize safety variables, using the study drug actually received.

#### **7.1.4. Pharmacokinetic Population (PK)**

The PK population will include all subjects in the SP who had at least one valid PK sample taken at any post-treatment timepoint. The PK population will be used to summarize PK variables, using the actual treatment a subject received.

### **7.2. Covariates and Subgroups**

#### **7.2.1. Planned Covariates**

Planned covariates include baseline values for the given assessment.

#### **7.2.2. Planned Subgroups**

Efficacy and safety variables related to eye assessments will be analyzed separately for the study eye and fellow eye, as appropriate. Other possible subgroups include age, sex, and race.

### **7.3. Management of Analysis Data**

#### **7.3.1. Data Handling**

For assessments collected at specific visits, the data from unscheduled visits will be included in the analysis of efficacy or safety if the data at the nearest scheduled visit is missing; all unscheduled visit data will be listed. All data from log pages (e.g., concomitant medications and AEs) will be included in the analysis tables.

#### **7.3.2. Missing Data**

For the analysis of the efficacy endpoints, observed values will be used; no imputation will be performed for missing efficacy data. Missing safety data will be imputed in limited cases, as described below.

##### **7.3.2.1. Handling of Missing Date Values**

###### Partial or Missing Dates

Missing portions of dates for AEs or concomitant medications will not be formally imputed. Instead, an AE will be classified as treatment-emergent or a medication as concomitant using the most conservative date that can be derived from the non-missing portion of the date.

##### **7.3.2.2. Missing Baseline Data**

Every effort will be made to ensure that accurate baseline information on the subjects is collected. In the event that a subject is missing baseline information, the subject will be included in the SP for assessment of safety and excluded from the primary analyses. Each case of missing baseline data will be evaluated for potential inclusion in the exploratory endpoints. All baseline data will be observed cases, without imputation.

#### **7.3.3. Handling of Early Termination Visit Information**

In the event that a subject is terminated early from this study, the early termination data will be assigned to the closest visit. If the closest visit has valid data, the early termination data will be assigned to the next available visit, and treated as observed data for that visit. For subjects who had efficacy measurements taken after the last dose, all observed measurements will be used for analyses.

#### **7.3.4. Coding Conventions for Events and Medications**

All AEs, medical and ophthalmic history, and concomitant procedures/therapies will be mapped to the Medical Dictionary for Regulatory Activities (MedDRA Version 25.0) system for reporting.

Prior and concomitant medications will be coded using WHO-DD (World Health Organization Drug Dictionary) (Version Global C3 2022-03-01).

### 7.3.5. Analysis Software

Data manipulation, tabulation of descriptive statistics, calculation of inferential statistics, and graphical representations will be performed using SAS (release 9.4 or higher) for Windows.

[figure not shown]
### 7.3.6. Study Data

Study data identified in the schedule for time and events (Table 1) are collected, and source verified, on the electronic data capture (EDC) [REDACTED] PK concentration data will be provided by [REDACTED].

All study data will be formulated into regulatory-compliant data sets to provide transparency, traceability, and integrity of trial analysis results from the collection source. Observed study data will be mapped to the Clinical Data Interchange Standards Consortium (CDISC) Study Data Tabulation Model (SDTM) and serve as the source data from the trial. All study analyses will be completed using analysis data sets that are derived from the SDTM and follow the CDISC Analysis Data Model (ADaM) architecture.

The methods for programming the CDISC SDTM and ADaM data sets are described in Figure 1.

**Figure 1 SDTM, ADaM, and TFL Development and Validation**

Where:

1. Development, validation, and maintenance of SDTM domains
2. Development and validation of ADaM data sets, with input source the appropriate SDTM domains.
3. Development and validation of tables, figures, and listings (TFL), with input data source the SDTM domains and analysis specific ADaM data sets.

#### **7.4. Planned Study Analyses**

##### **7.4.1. Statistical Summaries: Descriptive and Inferential**

Safety and efficacy endpoint results will be presented separately for Part 1 (Dose Escalation) and Part 2 (Optional Dose Expansion). For Part 1, [REDACTED] presented separately by treatment group (0.1% INV-102 BID, 0.25% INV-102 BID, 0.7% INV-102 BID, and 0.7% INV-102 TID), but vehicle subjects will be pooled across cohorts in the summaries. Categories for data presentation and analysis will consist of each treatment (INV-102 or Vehicle) and INV-102 dose level.

All p-values will be rounded to and displayed in four decimals. If a p-value less than 0.0001 occurs, it will be shown in tables as <0.0001. All statistical tests will be performed using a significance level of 5% (2-tailed). The p-values for the analysis of efficacy endpoints will be considered descriptive.

Descriptive summaries of variables will be provided where appropriate. For continuous variables, the number of non-missing values (n), mean, standard deviation, median, minimum, and maximum will be tabulated by treatment group. For categorical variables, the counts and proportions of each value will be tabulated by treatment group. Expansion of descriptive table categories within each treatment may occur if such elaborations are thought to be useful.

All study-related data collected will be presented in listings. Study-related data not subject to analysis according to this plan will not appear in any tables or graphs but will be included in the data listings.

##### **7.4.2. Interim Analyses and Data Monitoring**

[REDACTED]  
[REDACTED]  
[REDACTED]

After Part 1 (Dose Escalation) Cohorts 1 to 4 have been completed, the study may advance to the optional Part 2 based on review of available [REDACTED] data [REDACTED]

[REDACTED]  
[REDACTED].

##### **7.4.3. Final Analysis and Publication of Study Results**

The final analysis will be completed after all subjects have completed the study.

### **7.5. Multiple Testing Procedures**

There will be no adjustments for multiplicity and no formal multiple testing procedures are to be implemented with this analysis plan.

### **7.6. Baseline Values**

Baseline values are the values obtained prior to any drug administration at the Baseline Visit (Day 1). If the Day 1 value is missing or is not scheduled to be collected, any value collected prior to treatment administration (e.g., from the Screening visit) will be used as the baseline.

## **8. SUMMARY OF STUDY DATA**

### **8.1. Subject Disposition**

A summary of the analysis sets includes the number and percentage of subjects by treatment group and overall for the following categories: subjects in the SP, the mITT Population, the PP Population, and the PK Population. All percentages will be based on the number of randomized subjects.

End of trial information will also be summarized in this table, including the number of subjects completing the study, the number of subjects who prematurely discontinued the study with reasons for withdrawal, the number of subjects completing the study drug dosing, and the number of subjects who prematurely discontinued the study drug with reasons for study drug discontinuation.

A by-subject data listing of study completion information including the reason for premature study withdrawal or study drug discontinuation, if applicable, will be presented.

### **8.2. Protocol Deviations**

Major protocol deviations considered to have significant impact on treatment outcome will be determined by a Sponsor blinded review of the data. The Sponsor or designee will be responsible for producing the final deviation file; this file will include a description of the protocol deviation and clearly identify whether this violation warrants exclusion from the PP Population. This file will be finalized prior to database lock.

Protocol deviations will be presented in a by-subject data listing.

### **8.3. Demographics and Baseline Characteristics**

Subject demographic data and baseline characteristics will be tabulated and summarized descriptively by treatment group and overall. The demographic data and baseline characteristics will be summarized for the mITT, Safety, PP, and PK Populations.

The demographics consist of age (year), sex, race, ethnicity, and study eye. Age will be summarized using descriptive statistics. The number and percentage of subjects by sex, race, ethnicity, study eye will be presented. Percentages will be based on the total number of subjects in the study population presentation.

The following baseline characteristics will be summarized using descriptive statistics:

- Height
- Weight

#### **8.4. Medical History**

The number and percent of subjects with individual ophthalmic and general (non-ophthalmic) medical and surgical histories will be summarized for all subjects by treatment group and overall. Ophthalmic and general histories will be summarized separately.

Ophthalmic and general medical and surgical history will be coded using the MedDRA Version 25.0. The number and percentage of subjects with any ophthalmic and general medical history will be summarized and for each system organ class (SOC) and preferred term (PT). Percentages will be calculated based on number of subjects in the SP.

Ophthalmic and general medical history data including specific details will be presented in by-subject listings.

#### **8.5. Prior and Concomitant Medications**

A concomitant medication is defined as any medication taken on or after the day of first exposure to study drug. The number and percentages of all concomitant medications will be summarized by treatment group, Anatomical Therapeutic Chemical (ATC) level 2, and PT. The total number of concomitant medications and the number and percentages of subjects with at least 1 concomitant medication will be summarized by treatment group.

Prior medications are defined as any medication that has a start and stop date prior to the day of first exposure to study drug. Prior medications will be summarized the same way as for concomitant medications.

Prior and concomitant medication summaries will be performed using the SP.

#### **8.6. Treatment Exposure and Compliance**

The number of study drug exposure days will be calculated for each subject in the SP as the last date of study drug administration – first date of study drug administration. [REDACTED]

[REDACTED]  
[REDACTED]  
[REDACTED]  
[REDACTED]

Minimum study drug compliance (yes/no) for each subject in the SP will be determined as follows, depending on the study cohort:

- [REDACTED]  
[REDACTED]
- [REDACTED]  
[REDACTED]

■ [REDACTED]  
[REDACTED]  
[REDACTED]

[REDACTED]  
[REDACTED]

The number of study drug exposure days, exposure to study drug, and study drug compliance will be tabulated and summarized descriptively by treatment group and overall.

Treatment exposure and compliance will be presented in by-subject listings.

## 9. EFFICACY ANALYSES

Efficacy will be assessed using the mITT Population with subjects included in the treatment arm in which they were randomized. Primary and secondary efficacy endpoints will also be assessed using the PP Population. Efficacy results will be presented separately by cohort (Cohorts 1–5 as applicable). Data will be presented and analyzed by treatment group (INV-102 or Vehicle) and INV-102 dose level. Subjects assigned to vehicle in Cohorts 1–4 will be pooled across cohorts in the summaries.

All statistical tests will be performed using a significance level of 5% (2-tailed). The p-values for the analysis of efficacy endpoints will be considered descriptive. Observed cases will be used for all efficacy analyses—no imputation for missing values will be applied.

### 9.1. Primary Efficacy

The primary efficacy endpoint to be used in Part 2 was [REDACTED]  
[REDACTED] the Change from Baseline to Day 15 in the Eye Dryness Score from the [REDACTED] DED symptom VAS.

[REDACTED]  
[REDACTED]  
[REDACTED]  
[REDACTED]  
[REDACTED]

For Part 2 (Cohort 5), the primary efficacy endpoint, which is measured over multiple visits, will be summarized [REDACTED]. In addition, the Part 2 data will be analyzed using a mixed model for repeated measures (MMRM) that include treatment, visit, and treatment-by-visit interaction terms, and baseline eye dryness or eye discomfort VAS score as a covariate. The output from the MMRM will include the least-squares mean (LSM) and standard error for both treatment groups, along with the vehicle-corrected LSM, its 95% CI, and associated p-value. Include the average of study eye and fellow eye. LS mean values will also be displayed by visit and treatment group using line graphs.

[REDACTED]  
[REDACTED]  
[REDACTED]  
[REDACTED]

### 9.2. Secondary and Other Efficacy

Secondary and other efficacy endpoints are indicated in Section 4.1. [REDACTED]  
[REDACTED]  
[REDACTED]  
[REDACTED]  
[REDACTED]  
[REDACTED]  
[REDACTED]

Secondary and other efficacy data in Part 2 will be summarized [REDACTED]. In addition, Part 2 data will be analyzed using a similar MMRM as for the primary endpoint, with change from baseline as the dependent variable, treatment as factor, and the respective baseline value included as the covariate. The output from each MMRM will include the LSM and standard error for both treatment groups, along with the vehicle-corrected LSM, its 95% CI, and associated p-value.

[REDACTED]  
[REDACTED]  
[REDACTED]

If there are sufficient missing data, appropriate MI methods will be applied as described in Section 7.3.2.3.

## **10. SAFETY ANALYSES**

All safety analyses will be conducted using the SP. All safety analyses will be completed using the actual treatment a subject received. Observed case data will be used; no imputation will be performed for missing safety data except for the limited situations described in Section 7.3.2. Safety data will be tabulated and summarized descriptively by treatment group and for all subjects who took INV-102.

All safety data will be presented in by-subject listings.

### **10.1. Adverse Events**

AEs will be coded using MedDRA, Version 25.0.

Treatment-emergent adverse events (TEAEs) are defined as any AE that begins or worsens after initiation of the study drug. If the onset of an AE is on or after the date of first dose of study drug or is increasing in severity after first dose of study drug, then the AE will be considered treatment-emergent. Only TEAEs will be summarized in the tables.

The number and percent of subjects with any TEAEs will be summarized by SOC and PT by treatment group. At each level of tabulation (e.g., at the PT level), subjects will be counted only once if they had more than one such event reported during the AE collection period.

The following summary tables will be presented for TEAE data, by SOC and PT:

- TEAEs
- Serious TEAEs
- TEAEs leading to withdrawal from the study
- TEAEs leading to study drug discontinuation
- TEAEs by maximum severity (mild, moderate, severe)
- TEAEs by greatest relationship (not related, possibly related, or probably related).

All TEAEs and non-TEAEs will be presented in a by-subject listing.

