1.2.1 PART 1 (DOSE ESCALATION)

Screening Visit: Day -28 to Day -1

Total n=approximately 36 subjects

Procedures:

- Informed consent
- Inclusion/Exclusion criteria
- Demographics
- Ophthalmic medical and surgical history
- General medical and surgical history
- Concomitant medication review
- Urine pregnancy test (for women of childbearing potential)
- [REDACTED] DED symptom VAS
- Ophthalmologic assessments: visual acuity, [REDACTED] slit lamp exam [REDACTED]
[REDACTED] corneal fluorescein staining [REDACTED], and IOP
- AE assessment

Baseline/Initiation of Dosing Visit: Day 1

Cohorts (study drug will be dosed in both eyes in Part 1 regardless of whether they both meet the criteria as a Qualifying Eye):

- BID 0.1% Cohort: INV-102 (n=approximately 6) vs vehicle (n=approximately 3)
- BID 0.25% Cohort: INV-102 (n=approximately 6) vs vehicle (n=approximately 3)
- BID 0.7% Cohort: INV-102 (n=approximately 6) vs vehicle (n=approximately 3)
- TID 0.7% Cohort: INV-102 (n=approximately 6) vs vehicle (n=approximately 3)

Procedures:

- Inclusion/Exclusion criteria
- Concomitant medication review
- Vital signs (including height and weight)
- Urine pregnancy test (for women of childbearing potential)
- [REDACTED] DED symptom VAS
- [REDACTED]

- [REDACTED]
- [REDACTED]
- Ophthalmologic assessments: noncontact pachymetry, endothelial cell count, visual acuity, [REDACTED], slit lamp exam [REDACTED], corneal fluorescein staining [REDACTED] IOP, and dilated fundus exam
- [REDACTED]
- Randomization
- Study drug dispensing
- [REDACTED]
- Study drug administration by site staff
- [REDACTED]
- PK blood sample collection (pre-dose and at 5, 15, 30, 60, and 120 minutes post-dose)
- AE assessment

AE Assessment Telephone Visit: Day 2

- AE assessment

Mid-dosing Visit: Day 8 (±1 day)

Procedures:

- Concomitant medication review
- Vital signs
- [REDACTED] DED symptom VAS
- [REDACTED]
- [REDACTED]
- Study drug administration by site staff
- [REDACTED]
- [REDACTED]
- PK blood sample collection (pre-dose and at 5, 15, 30, 60, and 120 minutes post-dose)
- Ophthalmologic assessments (≥15 minutes AFTER administration of study drug): noncontact pachymetry, visual acuity, [REDACTED] slit lamp exam [REDACTED] corneal fluorescein staining [REDACTED] IOP, and dilated fundus exam
- [REDACTED]
- AE assessment

Completion of Dosing Visit: Day 15 (+1 day)

Procedures:

- Concomitant medication review

- Vital signs
- [REDACTED] DED symptom VAS
- [REDACTED]
- [REDACTED]

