9.2 ADVERSE EVENTS AND SERIOUS ADVERSE EVENTS

9.2.1 DEFINITION OF ADVERSE EVENTS

An AE is any untoward medical occurrence in a subject or clinical investigation participant administered a pharmaceutical product and that does not necessarily have a causal relationship with this study drug. An AE can therefore be any unfavorable and unintended sign (including an abnormal laboratory finding), symptom, or disease temporally associated with the use of a medicinal (investigational) product, whether or not related to that product.

All AEs that occur following consent and through the final study visit will be collected on the appropriate AE eCRF. All AEs recorded after starting study drug with the investigational product are considered TEAEs.

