9.2.4 TIME PERIOD AND FREQUENCY FOR EVENT ASSESSMENT AND FOLLOW-UP

The occurrence of an AE or SAE may come to the attention of study personnel during study visits and interviews of a subject presenting for medical care or upon review by a study monitor.

All AEs, including local and systemic reactions not meeting the criteria for SAEs, will be captured on the appropriate eCRF. Information to be collected includes event description, date of onset, clinician's assessment of severity, relationship to study drug (assessed only by those with the training and authority to make a diagnosis), and date of resolution/stabilization of the event. All AEs occurring while on study must be documented appropriately regardless of relationship.

Any medical condition that is present at the time that the subject is screened will be considered as baseline and not reported as an AE. However, if the subject's condition deteriorates at any time during the study, it will be recorded as an AE.

Changes in the severity of an AE will be documented to allow an assessment of the duration of the event at each level of severity to be performed. Adverse events characterized as intermittent require documentation of onset and duration of each episode.

Site staff will record all reportable events with start dates occurring any time after informed consent is obtained through the Follow-Up Visit. At each study visit, the investigator or designee will inquire about the occurrence of AE/SAEs since the last visit. All AEs will be followed for outcome information until resolution or stabilization or the subject's participation in the trial ends. All SAEs and those nonserious events assessed by the investigator as possibly or probably related to the study drug should continue to be followed even after the subject's participation in the trial is over. Such events should be followed until they resolve or until the investigator assesses them as "chronic" or "stable."

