10.3.4 SAFETY ANALYSES

All safety analyses will be conducted on the safety population using the following safety variables in Parts 1 and 2, unless as described below:

- Treatment-emergent AEs
- Vital signs
- Best-corrected visual acuity
- Slit lamp examination findings
- [REDACTED]
- Intraocular pressure (Part 1 only)
- Fundus examination (Part 1 only)
- Pachymetry (Part 1 only)
- Endothelial cell count (Part 1 only)
- Corneal fluorescein staining (Part 1 only)
- [REDACTED]

- [REDACTED]
- [REDACTED]
- [REDACTED]

Adverse events will be coded using the Medical Dictionary for Regulatory Activities (MedDRA; version 24.1). For each TEAE reported, the number and percent of subjects will be tabulated based on the preferred term. The tables will be generated by relationship to study drug as well as by system organ class and severity. Serious TEAEs and TEAEs leading to discontinuation of study drug and of study will also be summarized. Treatment-emergent AEs will be summarized; any AEs occurring after ICF signing but before initiation of study drug dosing will be presented in the listings but will not be summarized in tables.

Other safety endpoints will be summarized descriptively at each visit, showing actual values and change from Baseline values, where appropriate.

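### The date rule in SAP 10.1 counts adverse events that start on Day 1 before the first drop as TEAEs, against the SAP's own definition and Protocol 10.3.4

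*SAP*

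**What the plan says.** SAP 10.1 contains two statements. The definition is: "Treatment-emergent adverse events (TEAEs) are defined as any AE that begins or worsens after initiation of the study drug". The rule that decides classification follows it: "If the onset of an AE is on or after the date of first dose of study drug", or if severity increases after that dose, the event is treatment-emergent. The same section restricts the AE tables to TEAEs.

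Protocol 10.3.4 treats earlier events differently: "any AEs occurring after ICF signing but before initiation of study drug dosing will be presented in the listings but will not be summarized". The exclusion applies to the tables. Protocol 9.2.1 starts collection at consent ("All AEs that occur following consent and through the final study visit will be collected on the appropriate AE eCRF") and adds its own description: "All AEs recorded after starting study drug with the investigational product are considered TEAEs". On timing, Protocol 9.2.4 says "Information to be collected includes event description, date of onset" and goes on to other items; it names no time of onset.

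The Part 1 Day 1 list in Protocol 1.2.1 includes "Ophthalmologic assessments: noncontact pachymetry, endothelial cell count, visual acuity", then slit lamp, fluorescein staining, IOP and dilated fundus examination. All are listed ahead of randomization and dosing. SAP 7.6 takes baseline values from before any drug on Day 1.

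Protocol section 4 names TEAEs as the Part 1 primary endpoint. SAP 3.3 reports an added PK population and a redacted item, and otherwise claims agreement with the protocol's methods.

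**The concern.** The two statements in SAP 10.1 give the same answer for every AE except one that begins on Day 1 before the first drop. The definition excludes that event and the date rule includes it. A programmer will implement the date rule, because it can be computed from the onset date.

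The window is not empty. AEs are already being collected, and on that day every Part 1 subject has an eye examination that includes fluorescein, tonometry and, per Protocol 9.1, a dilating drop. A reaction to any of these carries the same calendar date as the first dose.

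What is at stake is the accuracy of the primary safety table of a first-in-human study with six active subjects per cohort, where individual events are read closely. An eye that has received no study drug could contribute a treatment-emergent ocular event.

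**Working it through.** **Step 1. Apply each rule to one case.** The case is an AE with onset on Day 1, known to precede the first drop, with no later worsening.

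| Source | Result |
|---|---|
| SAP 10.1, definition | Not a TEAE |
| SAP 10.1, date rule | TEAE, tabulated |
| Protocol 10.3.4 | Listing only |
| Protocol 9.2.1 | Depends on when the event was written down |

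SAP 10.1 therefore disagrees with itself, and its operative sentence disagrees with Protocol 10.3.4.

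**Step 2. Is the date rule only a fallback for incomplete dates?** No. SAP 7.3.2.1 has its own conservative rule for partial or missing dates. The rule in 10.1 also covers complete dates and makes no exception when the order is known.

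**Step 3. Are the Day 1 eye assessments really pre-dose?** The order of the list alone does not prove it: the pre-dose PK sample appears after drug administration in the same list. Two other places support it. SAP 7.6 defines baseline as pre-drug, and Protocol 1.2.1 marks the Day 8 and Day 15 ophthalmologic assessments as following administration by at least 15 minutes, with no such mark on Day 1.

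**Step 4. Size of one misclassified subject.** Inputs: 6 active and 3 vehicle per cohort and four cohorts (SAP 6); vehicle pooled across cohorts (SAP 7.4.1); a summary of all INV-102 subjects (SAP 10). Columns: 6 per active cohort, 4 × 3 = 12 pooled vehicle, 4 × 6 = 24 all active. The shift is 100/n percentage points:

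- active cohort: 100/6 = 16.7
- pooled vehicle: 100/12 = 8.3
- all Part 1 active: 100/24 = 4.2

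These apply to the any-TEAE row only if the subject has no other TEAE, because SAP 10.1 counts a subject once per level. The same holds within a preferred term.

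**Step 5. Chance of at least one such subject.** The documents give no rate, so p, the probability that a subject has a pre-dose Day 1 AE, is an assumption. The formula is 1 − (1 − p)^n.

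| Assumed p | n = 6 | n = 12 | n = 24 |
|---|---|---|---|
| 1% | 5.9% | 11.4% | 21.4% |
| 2% | 11.4% | 21.5% | 38.4% |
| 5% | 26.5% | 46.0% | 70.8% |
| 10% | 46.9% | 71.8% | 92.0% |

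For example, 1 − 0.99^6 = 5.9% and 1 − 0.90^6 = 46.9%. Under Protocol 10.3.4 these events would contribute nothing to the tables at any p.

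**Step 6. Direction.** An event before the first drop cannot depend on study drug, and assignment is randomized and masked. The expected excess is the same proportion in each arm, so absolute incidence rises and small columns become noisier, with no expected shift in the contrast.

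**The case against.** The strongest defence is that counting same-day events as treatment-emergent is a conservative convention, sensible when only a date is held and in keeping with SAP 7.3.2.1. That stands for events whose order is unknown, and the fix keeps it. It does not justify tabulating an event known to precede the drug, and SAP 10.1 does not present its rule as a convention.

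The SAP also limits the damage. TEAEs are tabulated by relationship, a pre-drug event should be graded as not related under Protocol 9.2.3.2, and every AE is listed by subject. This is true and helps a careful reader, but the event stays in the overall table and in the tables by organ class, preferred term and severity.

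Four stronger readings are tempting, and the documents do not support them:

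- *The rule distorted the choice of dose for Part 2.* That choice rests with unmasked personnel working under a separate plan (Protocol 5.2 and 10.3.6). The SAP's final analysis comes after all subjects finish (SAP 7.4.3). Nothing shows that tables built on SAP 10.1 were used.
- *The order of Day 1 events cannot be recovered.* The items in Protocol 9.2.4 are not stated to be exhaustive, and the eCRF is not available. The most one can say is that the named items do not include a time.
- *A screening-period event first written down at Day 8 becomes a TEAE.* The word 'recorded' in Protocol 9.2.1 invites this, but Protocol 10.3.4 works by occurrence and SAP 10.1 by onset or worsening, so the event would not be tabulated.
- *The deviation is undeclared.* SAP 3.3 has a redaction just before its consistency statement, so this can be said only of the readable text.

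**Conclusion.** The point holds as a stated rule that gives the wrong result for a definable set of events. SAP 10.1 would tabulate AEs that began on Day 1 before the first drop, although its own definition and Protocol 10.3.4 exclude them, and the table concerned is the Part 1 primary endpoint.

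The effect is over-counting of absolute incidence and noise. A reader might infer a biased comparison between INV-102 and vehicle; randomization gives no reason to expect one. A single affected subject is visible in columns of 6, 12 or 24, but how often this happens is unknown. The 1% to 10% range is illustrative: at its lower end the problem is unlikely in any one active cohort (about 6%), and at its upper end it is close to even (about 47%). The sizes also assume that the subject has no other TEAE in the row concerned. The contradiction itself rests on the text alone and needs no assumed rate.

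**What to change.** Change the date clause in SAP 10.1: an AE with onset on the date of first dose is treatment-emergent unless it is known to have started before the first instillation and did not worsen afterwards. If the order is unknown, it remains treatment-emergent. Known pre-drop events then go to the listings, as Protocol 10.3.4 requires.

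Establish the order in two ways:

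- *Subjects already seen.* The SAP cites a final CRF dated 08 August 2022 (SAP 3.1) and says the Part 2 endpoints were chosen from Part 1 results (SAP 4.1), so a new field comes too late for Part 1. Query sites, before database lock, on AEs with Day 1 onset. Site staff gave the first drop, so their notes may settle the order.
- *Subjects still to be dosed.* Add a flag for Day 1 AEs: before or after the first drop.

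In Protocol 9.2.1, replace 'recorded' by 'with onset or worsening', so that it agrees with 10.3.4.

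The cost is one SAP sentence, one protocol phrase, possibly one eCRF item and a few extra queries. Keeping the date rule and declaring it in SAP 3.3 would be cheaper and would remove the undeclared difference, but known pre-drug events would stay in the primary endpoint tables.
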